After completion of Induction Cycle 2 or Consolidation Cycle 1 (hereafter referred to collectively as Chemotherapy Cycle 2), subjects will undergo bone marrow aspiration for assessment of remission status at the investigative site. Bone marrow examination should await recovery of ANC to at least 1.0 \times 10⁹/L and platelet count to at least 100 \times 10⁹/L on or before but no later than Day 42 of Chemotherapy Cycle 2 unless leukemic progression is suspected. Subjects who achieve or remain in morphologic complete response (CR) after Chemotherapy Cycle 2 will undergo measurable residual disease (MRD) assessment in peripheral blood and bone marrow aspirate. Subjects who have not achieved morphologic CR last cycle of induction chemotherapy (no later than Day 42 of the last cycle of induction) will be considered treatment failures. *For subjects with < 5% residual blasts post-Induction Cycle 1, Consolidation Cycle 1 will consist of Chemotherapy Cycle 2. For patients with \geq 5% residual blasts post-Induction Cycle 1, Induction Cycle 2 (**Table 1**) will consist of

Chemotherapy Cycle 2 with consolidation beginning thereafter. All subjects are eligible to receive up to 3 cycles of high dose cytarabine after Chemotherapy Cycle 2.

Figure 1 provides a schematic representation of the study treatment plan from Cycle 1 Day 1 through completion of Chemotherapy Cycle 2

Table 1: Induction Chemotherapy

	Age < 60 years	Age ≥ 60 years
Cycle 1:		
Cytarabine ^a	100 mg/m ² by continuous infusion, Days 1-7	100 mg/m ² by continuous infusion, Days 1-7
Anthracycline	Daunorubicin, 60 mg/m ² slow IV push, Days 1-3 OR Idarubicin, 12 mg/m ² slow IV push, Days 1-3	Daunorubicin, 60 mg/m ² by slow IV push, Days 1-3 OR Idarubicin, 12 mg/m ² slow IV push, Days 1-3
Cycle 2:		
Cytarabine	1.0 g/m ² , BID Days 1-6	1.0 g/m ² , BID Days 1-6
Anthracycline	Daunorubicin, 60 mg/m ² slow IV push, Days 1-3 OR Idarubicin, 12 mg/m ² slow IV push, Days 1-3	N/A

Abbreviations: BID, twice daily; IV, intravenous; N/A, not administered.

^a Subjects who are candidates for continuous infusion of cytarabine in Cycle 1 at doses higher than 100 mg/m²/day are ineligible.

Subjects who achieve MRD negative CR status post-induction will undergo retrospective MRD assessments in peripheral blood every 3 months until morphologic relapse.

[figure not shown]

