All subjects who achieve morphologic CR, complete response with hematologic improvement (CRh), or complete response with incomplete blood count recovery (CRI) upon completion of Chemotherapy Cycle 2 may initiate or continue consolidation therapy in combination with ENTO or placebo as outlined in Table 2 at the investigator's discretion either instead of or as a bridge to hematopoietic stem cell transplant (HSCT).

Table 2: Treatment Phase - Consolidation

	Age < 60 years	Age \geq 60 years
Cytarabine	3.0 g/m ² , BID over 3 hours on Days 1, 3 and 5 every 28-35 days for up to 3 cycles*	1.5 g/m ² , BID over 3 hours on Days 1, 3 and 5 every 28-35 days for up to 3 cycles*

*For subjects with < 5% residual blasts post-Induction Cycle 1, Consolidation Cycle 1 will consist of Chemotherapy Cycle 2. For patients with \geq 5% residual blasts post-Induction Cycle 1, Induction Cycle 2 (Table 1) will consist of Chemotherapy Cycle 2 with consolidation beginning thereafter. All subjects are eligible to receive up to 3 cycles of high dose cytarabine after Chemotherapy Cycle 2.

Figure 1: Treatment Phase- Cycle 1, Day 1 through Completion of Chemotherapy Cycle 2:

* Following recovery of ANC to $>1.0 \times 10^9 /L$ and platelet count to $>100 \times 10^9 /L$
BMA, bone marrow aspirate; MRD, measurable residual disease

Following completion of consolidation chemotherapy, all subjects will undergo an End-of-Study Treatment Visit 30 ± 7 days after the last study treatment (either ENTO/placebo or cytarabine, whichever is later) or prior to initiation of follow-on therapy (e.g., maintenance therapy, HSCT) if sooner than 30 ± 7 days after last study treatment.

All subjects regardless of their post-remission status will be followed monthly for 3 months after the End-of-Treatment Visit and thereafter at least once every 3 months for progression/relapse, first salvage therapy, and survival until study termination. Unscheduled study visits at other time points

are permitted in the setting of suspected leukemic recurrence or for evaluation and management of post-treatment sequelae.

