Days on Study is the number of days from C1D1 to the date of completion or study discontinuation on the End of Study page of the CRF.

Cumulative Dose of ENTO

Cumulative dose of ENTO is defined as the sum of the doses administered to a patient measured in milligrams (mg). For subjects receiving placebo, this is set to 0 mg.

Cumulative Dose of Chemotherapy

The cumulative dose of each chemotherapy agent is defined as the sum of the doses administered to a patient measured in milligrams per meter squared (mg/m^2). Cumulative chemotherapy administration will be calculated separately for Induction and Consolidation.

Actual Dose Intensity (mg/m²)

The actual dose intensity will be defined separately for each chemotherapy component by phase (Induction, Consolidation) and treatment cycle (as the cumulative dose / duration).

Relative Dose Intensity

Relative dose is set to 100*(Actual Dose Intensity/ (Expected Cumulative Dose / 28)).

Completed Chemotherapy Cycle

A chemotherapy cycle is considered completed if at least one of the assigned chemotherapy agents in the regimen has been completed per protocol. Information regarding premature discontinuation of chemotherapy will be as recorded on the Study treatment – IV administration pages of the CRF.

Response Criteria

Criteria for responses as outlined below and assessed by the investigator are based on the ELN 2017 definitions (Döhner et al 2017) with minor modification for neutrophil and platelet count thresholds as defined by the IWG and as applicable to the current study:

CR*

CR requires all the following:

- Bone marrow blasts < 5%
- Absence of circulating blasts and blasts with Auer rods
- Absence of extramedullary disease (i.e., leukemia outside of bone marrow confirmed by biopsy)
- Absolute neutrophil count > 1.0 x 10⁹/L (1000/µL)
- Platelet count > 100 x 10⁹/L (100,000/µL)

*Note: *MRD positive or unknown*

Complete Response with Hematologic Improvement (CRh)**

CRh requires all the CR criteria, except for residual thrombocytopenia and/or neutropenia and is defined as:

- Bone marrow blasts < 5%
- Absence of circulating blasts and blasts with Auer rods
- Absence of extramedullary disease
- Absolute neutrophil count > 0.5 x 10⁹/L (500/µL)
- Platelet count > 50 x 10⁹/L (50,000/µL)

Complete Response with Incomplete Blood Count Recovery (CRi)**

CRi requires all the CR criteria, except for residual neutropenia or thrombocytopenia and is defined as:

- Bone marrow blasts < 5%

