6.3. Exposure to Treatment

The number of days on oral study drug and cumulative dose will be summarized by treatment group for the Safety Analysis Set. Additionally, the number of chemotherapy cycles completed and the relative dose intensities for each chemotherapy agent will be presented by treatment group, separately for Induction and Consolidation and presented by cycle and overall. Drug administration details will be listed.

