10. PROPOSED TABLES, LISTINGS, AND FIGURES

Summary Tables

- 1 Subject Disposition
- 2 Demographics and Baseline Disease Characteristics
- 3 Exposure to Study Medication and Chemotherapy
- 4 Summary of Responses after Two Cycles of Chemotherapy
- 5 Summary of Treatment-Emergent Adverse Events by System Organ Class, Preferred Term, and Greatest Severity
- 6 Summary of Treatment-Related Adverse Events by System Organ Class and Preferred Term
- 7 Summary of Serious Treatment-Emergent Adverse Events by System Organ Class and Preferred Term
- 8 Summary of Treatment-Emergent Adverse Events by System Organ Class and Preferred Term
- 9 Summary of Treatment-Emergent Severity Graded Laboratory Abnormalities

Figures

- 1 Chemistry Parameters Over Time
- 2 Hematology Parameters Over Time

Data Listings

- 1 Subject Disposition
- 2 Treatment-Emergent Adverse Events
- 3 Treatment-Emergent Severity Graded Laboratory Abnormalities
- 4.1 Demographics
- 4.2 AML Diagnosis
- 5.1 Study Treatment - IV/Infusion Administration Details
- 5.2 Study Treatment - Oral Administration Details
- 6 Response Assessment after Two Cycles of Chemotherapy
- 7 Vital Signs, Height, and Weight
- 8 Electrocardiogram
- 9 Physical Examinations
- 10 ECOG Performance Status
- 11 Echocardiogram/MUGA for LVEF Assessment
- 12 General Medical History
- 13 Prior and Concomitant Medications
- 14 Prior Leukemogenic Agent Exposure

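### The SAP counts a two-agent chemotherapy cycle as completed when only one agent was completed, so the completed-cycle count alone cannot show partial induction cycles

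*SAP*

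**What the plan says.** The definition of a completed cycle is in SAP Section 4.4.4: "A chemotherapy cycle is considered completed if at least one of the assigned chemotherapy agents in the regimen has been completed per protocol". The next sentence there takes information on premature discontinuation from the IV administration CRF pages and does not alter the rule.

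The definition is used in SAP Section 6.3, where "the number of chemotherapy cycles completed and the relative dose intensities for each chemotherapy agent will be presented by treatment group". Results are shown separately for Induction and Consolidation, by cycle and overall. Going by its title, the output that carries the count is Summary Table 3 in Section 10, "Exposure to Study Medication and Chemotherapy".

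SAP Section 2.1 gives the regimens. In Induction Cycle 1, at all ages, cytarabine runs "by continuous infusion, Days 1-7" and the anthracycline is given by "slow IV push, Days 1-3". Induction Cycle 2 pairs six days of twice-daily cytarabine with three days of anthracycline under age 60, and is cytarabine alone from age 60. Consolidation is cytarabine alone, "BID over 3 hours on Days 1, 3 and 5 every 28-35 days for up to 3 cycles".

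**The concern.** A reader of an exposure table will take a completed cycle to mean that the regimen was given. Under this rule it means only that one component was finished. In the two-agent cycles the anthracycline ends on Day 3, before cytarabine does. Once those three doses are in, no later stopping of cytarabine can change the cycle's status. The reverse also holds: full cytarabine with some or all of the anthracycline omitted counts as completed.

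Early stopping of cytarabine is a case the protocol provides for. Section 6.5.2 covers stopping it within a cycle for neurotoxicity. That section's heading refers to consolidation, but Section 8.6.1 and footnote d of Table 7 also point to it for induction dosing.

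What is at stake is how one descriptive row reads. After early termination the SAP exists to produce the safety analyses for an abbreviated study report, and exposure to the chemotherapy backbone is part of that report.

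**Working it through.** The plan states no figure for this item, so there is nothing to reproduce. The check applies the SAP's rule to the SAP's own schedules.

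**1. Which cycles the rule can misdescribe**

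| Cycle | Assigned agents | Does at least one differ from all? |
|---|---|---|
| Induction 1, all ages | cytarabine + anthracycline | yes |
| Induction 2, age <60 | cytarabine + anthracycline | yes |
| Induction 2, age ≥60 | cytarabine | no |
| Consolidation, all ages | cytarabine | no |

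**2. How incomplete a completed cycle can be.** Share of plan = amount given / amount planned.

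- Induction Cycle 1, anthracycline complete, cytarabine stopped after Day 3: planned 7 × 100 = 700 mg/m², given 3 × 100 = 300 mg/m², so 300/700 = 42.9%.
- Induction Cycle 1, cytarabine complete, with 0, 1 or 2 of 3 anthracycline doses: 0%, 33.3% or 66.7% of the planned anthracycline.
- Induction Cycle 2, age <60, anthracycline complete, cytarabine stopped after Day 3: 6 of 12 doses = 50%.

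All of these count as completed under the SAP rule. None would under a rule requiring every assigned agent.

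**3. Whether relative dose intensity (RDI) reveals the shortfall.** SAP Section 4.4.4 defines actual dose intensity by agent, phase "and treatment cycle (as the cumulative dose / duration", and then: "Relative dose is set to 100*(Actual Dose Intensity/ (Expected Cumulative Dose / 28". Hence RDI = 100 × (cumulative dose / duration) / (expected cumulative dose / 28). Duration is not defined. For Induction Cycle 1 cytarabine the expected term is 700/28 = 25 mg/m² per day.

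| Reading of duration | 3 of 7 days given | 7 of 7 days given |
|---|---|---|
| 28-day cycle | (300/28)/25 = 42.9% | (700/28)/25 = 100% |
| 42-day cycle | (300/42)/25 = 28.6% | (700/42)/25 = 66.7% |
| dosing days | (300/3)/25 = 400% | (700/7)/25 = 400% |

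Read as cycle length, RDI registers the truncation, although it mixes truncation with delay. Two of three anthracycline doses in a 28-day cycle give 66.7%, and so do all three in a 42-day cycle: (3/42)/(3/28) = 66.7%. Read as dosing days, RDI does not register the truncation at all.

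**4. Size in the table.** SAP Section 4.2 gives 15 randomised subjects. The split by arm is not stated. Assuming 7 and 8, and assuming a percentage is displayed, one reclassified subject moves an arm by 1/8 = 12.5 or 1/7 = 14.3 percentage points. How many real cycles would be reclassified cannot be worked out from the documents.

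**The case against.** The strongest reply is that nothing is concealed. Section 6.3 puts RDI for each agent beside the count, by arm and by cycle. Listing 5.1 gives the IV administration details, and with 15 subjects a reader can check every cycle. Reading duration as dosing days is implausible, because it gives 400% even for a fully dosed cycle and sits badly with the formula's own 28-day denominator. The definition is stated openly, and no protocol definition contradicts it. An all-agents rule is also coarse: one missed anthracycline dose and near-total omission would both become not completed.

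Much of this stands. A reader might infer that the rule hides partial cycles and any difference between arms in them. The documents do not support that, because RDI under its natural reading and Listing 5.1 both carry the information. Nor do they support treating cycle completion as a central tolerability endpoint. The safety endpoints named in protocol Section 3.0 and SAP Section 3 are adverse events, laboratory values, ECG, ECHO/MUGA and ECOG status. A reader might also suppose that the definition decides who enters the response summary after two cycles. Nothing in the SAP says so.

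The narrower point survives. The count itself is misleading for two-agent cycles, and recovering the true figure means rebuilding it from a listing. The adverse-event summaries do not fill the gap: Section 6.5.1 covers events leading to changes in ENTO/placebo, and Section 10 plans no table of events leading to discontinuation of chemotherapy. The coarseness of an all-agents rule is a reason to add a partial-cycle row or to report by agent. It is not a reason to keep the present rule.

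**Conclusion.** The concern holds as a minor reporting point. The completed-cycle count would include two-agent induction cycles in which the second agent was stopped early or not given, and the count alone does not show them. RDI (with duration taken as cycle length) and Listing 5.1 partly make up for this.

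The reach is small. The row is descriptive, no statistical inference is planned (SAP Section 4.4.3), and no protocol-defined primary or secondary efficacy endpoint is analysed (Section 6.4). At most 15 subjects are involved, and the size of the Safety Analysis Set used for the exposure table is not given. Whether any cycle was actually truncated is unknown, and the number may be zero. The shift of 12.5 to 14.3 points per subject rests on an assumed 7/8 split and an assumed percentage display; the SAP specifies a number of cycles, not a rate.

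**What to change.** In SAP Section 4.4.4, define a completed cycle as one in which all assigned agents were completed per protocol. In Table 3, either add a row for partially completed cycles (at least one but not all assigned agents completed) or report completion separately for each agent. Because the definition refers to assigned agents, Induction Cycle 2 from age 60 needs no special handling, and consolidation counts do not change.

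The cost is one SAP sentence and one table row. The data are already collected on the IV administration CRF pages, and the final analysis follows database lock (SAP Section 4.5). Stating in the same edit that duration means cycle length would make RDI a more dependable companion to the count. This changes reporting only; no dose or treatment rule is affected.

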4.4.5. Presentations by Study Visit

All study visits should be scheduled relative to C1D1 regardless of any treatment interruptions. Visits will be presented according to the visit designation as recorded in the CRF. Unscheduled and Early Termination Visits will be excluded from visit presentations. All data will be presented in data listings.

4.4.6. Missing Data

Every effort will be made to obtain required data at each scheduled evaluation from all subjects who have been randomized. In situations where it is not possible to obtain all data, it may be necessary to impute missing data. AEs with missing causal relationship will be assessed as related to study treatment. AEs with missing severity will be included in the denominator for all grade events of the same preferred term (PT) but will not be included in the numerator for any severity when reporting the frequency of events by severity. See [Section 4.4.4.4](#) for details of imputing missing dates. See [Section 6.4](#) for details of imputing missing efficacy endpoints.

Unless otherwise specified, all other missing data will not be imputed.

4.4.6.1. Imputation for Alphanumeric Data

Should there be instances where a clinical laboratory parameter is reported with imbedded non-numeric characters, such as, for example, “<0.1” or “>10”, the data will be imputed for quantitative summaries. The actual values as reported in the database will be presented in data listings.

For incorporation in quantitative summaries, the following imputation rules will be employed:

The limit of quantitation will be increased by one level of precision in the direction of the symbol that precedes the value. For example, “<0.1” will be imputed to “0.09”, while “>0.1” will be imputed to “0.11”, and “>10” will be imputed to “10.1”.

4.4.6.2. Incomplete or Missing Dates

An incomplete date occurs when the exact date an event started or ended cannot be obtained. The database contains data fields for month, day, and year. A date is incomplete if at least one of these three fields is not known.

For many of the planned analyses, a complete date is necessary to determine if the event should be included in the analysis (i.e., if the event is treatment-emergent) or to establish the duration of an event. In such cases, incomplete or missing dates will be imputed.

For the purposes of handling partially reported start and stop dates for an event the following algorithm will be applied:

- Missing start day, but month and year present:

If the event occurs in the same month and year as the initiation of study treatment, then the start day of the event will be assigned to C1D1. For example, if an AE occurred in December 2021, and C1D1 study treatment administration was on 8 December 2021 then the date of AE onset would be set to 8 December 2021.

Otherwise, the start day will be set to the first day of the month.

- Missing start day and month, but year present:

If an event occurs in the same year as the initiation of study treatment, then the start date of the event will be assigned to C1D1. For example, in the event a subject started study treatment on 20 January 2022 and had an AE starting in 2022 with no Month and Day indicated, the AE date would be set to 20 January 2022.

Otherwise, the start day and month will be set to 01 January. Thus, for AEs with a start date of 2022 and initiation of study treatment in 2021, the AE start date would be 01 January 2022.

- Missing start day, month, and year will be set to C1D1.

- Missing end day, but month and year present:

The day will be set to the last day of the month.

- Missing end day and month, but year present:

The end day and month will be set to 31 December of that year or the study treatment completion date, if earlier.

If any imputed date causes the end date to occur prior to the start date of the event, the start date of the event will be used for the imputation of the end date. In subject data listings, start and stop dates of events will be displayed as reported on the CRF (i.e., imputed values will not be listed).

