8.11.1 Time Period for Reporting AEs and SAEs

During the period from signing informed consent for this study until initiation of study treatment, only SAEs will be reported. Beginning on Day 1 of Cycle 1 all AEs, and SAEs will be reported through 30 days after treatment completion. Thereafter, only SAEs that are study medication related as assessed by the investigator will be reported.

Prompt notification by the investigator to the sponsor of an SAE is essential so that legal obligations and ethical responsibilities are met. All SAEs will be reported to the sponsor or designee immediately, without undue delay, as outlined in [Appendix 2](#). The investigator will submit any updated SAE data to the sponsor immediately, without undue delay.

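### SAP 4.4.6.2 sets an incomplete start date to C1D1 without checking the end date, so an SAE known to have resolved before treatment can be counted as treatment-emergent

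*SAP*

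**What the plan says.** SAP 4.4.6.2 has three branches that put an incomplete start date on C1D1.

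- Day missing, month and year the same as C1D1: "then the start day of the event will be assigned to C1D1".
- Day and month missing, same year: "If an event occurs in the same year as the initiation of study treatment, then the start date of the event will be assigned to" the same date, C1D1.
- Nothing known: "Missing start day, month, and year will be set to C1D1".

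A partial start in another month or year goes to the first of that month, or to 1 January. The section closes with a conflict rule. Its trigger is "If any imputed date causes the end date to occur prior to the start date of the event", and its action is that "the start date of the event will be used for the imputation of the end date". Listings are to show dates as recorded on the CRF.

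SAP 4.4.4 defines a TEAE by onset or worsening between C1D1 and 30 days after study treatment ends; the end date of the event is not used. The same section calls a medication prior if it was stopped before study treatment began, and concomitant if it was taken on or after that point.

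Protocol 8.11.1 says that between consent and first treatment "only SAEs will be reported".

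**The concern.** Putting an uncertain onset on C1D1 is a sensible cautious convention when nothing else is known. It is not sensible when the record itself shows that the event was over before C1D1. Nothing in the three branches tells the programmer to look. The imputed start is then enough to make the event treatment-emergent, against information already in the database.

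This matters more than usual here because safety is nearly all that remains of the analysis. SAP 6.4 drops the protocol's efficacy endpoints, and the main outputs are the TEAE and serious TEAE tables (SAP Section 10, Tables 5 to 8) on a study that stopped at 15 randomized subjects. The error can only add events to those tables.

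**Working it through.** **Inputs.** Start, end and conflict rules: SAP 4.4.6.2. TEAE, prior and concomitant definitions: SAP 4.4.4. Pre-treatment reporting: Protocol 8.11.1. Screening of 14 days from consent: Protocol 8.1. Final size of 15: SAP 4.2.

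**Rule as coded.** S is the start and E the end.

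- S = C1D1 in the three branches above; otherwise the first of the known month, or 1 January of the known year.
- E = last day of the month if only the day is missing; 31 December or study treatment completion, if earlier, when day and month are missing.
- Conflict rule, broad reading: if E < S, then E is set to S.
- Treatment-emergent if C1D1 ≤ S ≤ end of study treatment + 30 days. E does not enter.

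**The SAP's own examples first.** An AE in December 2021 with C1D1 on 8 December 2021 gives S = 8 December 2021, matching the text ("then the date of AE onset would be set to 8 December 2021"). An AE in 2022 with C1D1 on 20 January 2022 gives 20 January 2022. An AE in 2022 with treatment started in 2021 gives 1 January 2022. All three are reproduced. None of the examples includes an end date.

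**Records with an end before C1D1.** C1D1 is 8 December 2021 except in (d), where it is 20 January 2022. TE/con means treatment-emergent or concomitant; the last column applies the condition given under the fix.

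| Case | Start recorded | End recorded | S and E under the SAP | Status | S and E with the condition |
|---|---|---|---|---|---|
| (a) | Dec 2021 | 5 Dec 2021 | 8 Dec, 8 Dec 2021 | TE/con | 1 Dec, 5 Dec 2021 |
| (b) | 2021 | 10 Mar 2021 | 8 Dec, 8 Dec 2021 | TE/con | 1 Jan, 10 Mar 2021 |
| (c) | missing | 1 May 2019 | 8 Dec, 8 Dec 2021 | TE/con | 1 May, 1 May 2019 |
| (d) | 2022 | 12 Jan 2022 | 20 Jan, 20 Jan 2022 | TE/con | 1 Jan, 12 Jan 2022 |
| (e) | 2021 | Nov 2021 | 8 Dec, 8 Dec 2021 | TE/con | 1 Jan, 30 Nov 2021 |
| (f) | Nov 2021 | 5 Dec 2021 | 1 Nov, 5 Dec 2021 | before treatment | unchanged |
| (g) | 2 Dec 2021 | 5 Dec 2021 | 2 Dec, 5 Dec 2021 | before treatment | unchanged |

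With the condition, cases (a) to (e) all become pre-treatment or prior, and the SAP's three examples do not change.

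**Which of these can be study SAEs.** Cases (a) and (d) end 3 and 8 days before C1D1, inside a 14-day screening period. Cases (b) and (c) ended long before consent, so they could only be medications. If C1D1 is spread evenly over the days of 2022, the mean of min(day of month − 1, 14)/14 is 0.75: about three quarters of screening days share C1D1's calendar month. A screening SAE with an unknown start day would therefore often meet the first branch.

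**Does the conflict rule matter?** On the broad reading, case (a) becomes 8 to 8 December. On the narrow reading (only imputed end dates move), S is still 8 December and E stays 5 December, so the record ends three days before it begins. It is treatment-emergent either way.

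**Size for one subject.** 100 × 1/15 = 6.7 points over all randomized subjects; 100 × 1/8 = 12.5 and 100 × 1/7 = 14.3 points in arms of 8 and 7.

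**The case against.** The strongest reply is that the algorithm should never reach these records. SAP 4.4.6.2 introduces imputation for cases where a complete date is needed, for instance to settle whether an event is treatment-emergent. An end date before C1D1 already settles that. This is a fair account of what the authors probably meant, but the branches themselves carry no such condition. The same introduction also gives event duration as a reason to impute, and that would bring a record with a partial start and a known end back in. A programmer following the text would assign C1D1.

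A second reply concerns the conflict rule. A complete, reported end date is not being imputed, so the closing sentence need not touch it. That reading is open; the trigger, which covers any imputed date, points the other way. The sentence is ambiguous. A reader might infer that overwriting the end date is what creates the false TEAE. The documents do not support that: the TEAE definition ignores the end date, so the start rule does it alone, and the closing sentence at worst hides the conflict.

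Three further points stand.

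- Listings keep the recorded dates, so it would be too strong to say that reported data are lost. Listing 2 (TEAEs) would show such an event with an end before C1D1.
- The rule speaks of events and does not name medications, although it is the SAP's only date-imputation rule. A recorded stop before treatment already makes a drug prior, and medications are only listed (SAP 6.5.3). The most that could go wrong is a label in that listing.
- The rule treats both arms alike and no testing is planned (SAP 4.1, 4.4.3), so nothing here shows bias between arms.

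**Conclusion.** The start-date rule is wrong as written: it can count as treatment-emergent an SAE that the record shows was over before treatment. The point is minor. It needs an SAE between consent and first treatment, a start that falls into one of the three C1D1 branches, and an end before C1D1. The schedules of assessments mark AEs at Screening, but Protocol 8.11.1 limits what is reported then to SAEs. No affected record is known.

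The 6.7 points, and the 12.5 to 14.3 points by arm, are ceilings and not estimates. They require that the affected subject has no other event counted in the same row. The by-arm figures also assume arms of 8 and 7, inferred from 1:1 randomization of 15; the SAP does not give arm sizes, and the Safety Analysis Set groups subjects by treatment received.

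**What to change.** Add to SAP 4.4.6.2, in substance:

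- Assign C1D1 as the start only if the end date is missing, the event is ongoing, or the end date could fall on or after C1D1. A partial end in C1D1's own month therefore stays under the present rule.
- If the end date, full or partial, is certainly before C1D1, the event is not treatment-emergent and, where the rule is used for medications, the medication is prior. Impute the start as the earliest date that fits the recorded parts and is not later than the end date. If the start is wholly missing, use the end date.
- The conflict rule may move only imputed end dates, never a complete reported one.
- State whether the section applies to medications.

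The cost is a few SAP sentences and one program condition. If outputs already exist, checking Listing 2 for recorded ends before C1D1 would show whether any table needs to change; with 15 subjects this can be done by eye.
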